2.2. Hypothesis

It is hypothesized that treatment with daratumumab results in an ORR of >30% versus a null hypothesis of at most 15% in relapsed or refractory NKTCL, nasal type subjects failed (relapsed or refractory after achieving complete or partial remission) at least one line of chemotherapy.

3. STUDY DESIGN AND RATIONALE

3.1. Overview of Study Design

This is an open label, single arm, multicenter, Phase 2 study to evaluate the efficacy and safety of daratumumab monotherapy in subjects with relapsed and refractory extranodal NKTCL, nasal type. The study is a Simon's 2-stage design with up to 32 subjects to be enrolled. Following that, additional patients (ie, approximately 35 patients) may be enrolled in an expansion phase.

Subject participation will include a Screening Phase, a Treatment Phase, and a Follow-up Phase. The Screening Phase will be up to 21 days prior to Cycle 1, Day 1. Prior to enrollment, diagnosis of NKTCL must be verified by the sponsor from the local pathology report. Before enrollment to the study, sites will be required to provide archival or fresh tumor samples for assessment of CD38 expression. Fresh biopsy samples are preferred if available. Otherwise, archived formalin-fixed, paraffin-embedded (FFPE) blocks/slides are also acceptable.

The Treatment Phase will extend from Cycle 1, Day 1 until study drug discontinuation. After the first dose, disease evaluations will occur every 8 weeks for the first 6 months and thereafter, every 16 weeks. Subjects will be monitored for safety and assessed for PK and immunogenicity according to the scheduled assessments in the Time and Events (T&E) schedules ([T&E Schedule](#) and [T&E Schedule: PK and Immunogenicity](#)). Subjects will be treated until PD, unacceptable toxicity, or other reasons as listed in the protocol. End-of-Treatment (EoT) Visit is to occur within 30 days (+7-day window) after the last dose of all study treatments.

The Follow-up Phase will begin once a subject discontinues study treatment, and will continue until death, lost to follow up, consent withdrawal for study participation, or end of study, whichever occurs first. The follow-up schedule is presented in the [T&E Schedule](#).

The study is a Simon's 2-stage design with an interim analysis conducted after approximately 15 subjects have received at least one dose of study drug and had at least one post-baseline disease evaluation. The purpose of the interim analysis is to evaluate efficacy and safety data in stage 1 and facilitate the early preparation for the next step of development. The totality of efficacy (ORR), safety, and biomarker data will be analyzed at the interim. Enrollment may be put on hold pending the decision of interim analysis unless the decision is clear based on available data before the interim analysis. The futility criteria are defined in Section 10.9. The study may be terminated if the futility criteria are met and supported by totality of data. In addition, at interim, the association between daratumumab activity and CD38 expression level will be explored. A population enrichment strategy may be applied after the interim analysis if such a strategy is supported by emerging data. The primary analysis will be performed at approximately 6 months after the last subject receives the first dose of daratumumab.

The end of study is defined as approximately 9 months after the last subject receives the first dose of daratumumab. After study completion, the sponsor will ensure that subjects who are currently on treatment and receiving benefit, will continue to receive daratumumab until PD, unacceptable toxicity or other.

Assessment of tumor response and PD will be based on BICR in accordance with the Revised Criteria for Response Assessment - LUGANO Classification.¹²

Subjects will be monitored for safety during the Screening and Treatment Phases and up to 30 days after the last dose of study drug. Adverse events (AE), including laboratory AEs, will be graded and summarized using National Cancer Institute Common Terminology Criteria for Adverse Events (NCI-CTCAE), version 4.03. Measures to prevent infusion-related reactions will include preinfusion medication with methylprednisolone, acetaminophen (or paracetamol), and

an antihistamine before each daratumumab infusion. Blood samples will be drawn for assessment of PK, immunogenicity, and biomarkers.

Additional patients (ie, approximately 35 patients) may be enrolled in an expansion phase to confirm the clinical response rate of daratumumab if supported by emerging data.

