3.2. Study Design Rationale

Daratumumab Dose Rationale

An established dose regimen of 16 mg/kg (weekly for 8 weeks, then every 2 weeks for 16 weeks, then every 4 weeks thereafter), administered via IV until PD or unacceptable toxicity, was selected based on an acceptable safety profile, clinical activity, and pharmacokinetics consistent with saturation of the target (CD38).

Rationale for Pharmacokinetics and Immunogenicity

Data obtained from the current study will provide information about the pharmacokinetic profile of daratumumab in subjects with NKTCL.

Immunogenicity to daratumumab is possible. Therefore, samples to determine the presence of antibodies to daratumumab (immunogenicity) will be collected from all subjects. The pharmacokinetic assessments collected at all immunogenicity time points will be used to interpret the immunogenicity data. The information from these samples and data from other studies will be used to determine the immunogenicity of daratumumab.

Biomarker Collection

Biomarkers collected in this study will evaluate tumor CD38 levels as a predictive marker of response. Exploratory analysis of Complement Inhibitory Proteins (CIPs, such as CD59, CD55 and CD46) expression from previous studies has indicated that high expression of CIPs might be predictive of lower or lack of response to daratumumab. Therefore, samples collected in this study might evaluate both CD38 and CIPs expression levels by immunohistochemistry (IHC) or immunofluorescent staining. CD38 IHC is a mandatory test, and CIPs staining will be performed whenever samples are available. Specific immune cell subtypes (NK cells, T cells, and B cells) and their subtypes will be analyzed to evaluate the effects of daratumumab on immune cells. This will provide information on potential prognostic markers in NKTCL to better understand this disease, as well as potential markers that predict response to daratumumab.

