Any AE deemed to be related to daratumumab that requires a dose hold of more than 4 weeks (Cycle 1 to Cycle 6) or more than 6 weeks (Cycle 7 and beyond) will result in permanent discontinuation of daratumumab. If a dose delay occurs, then PK and pharmacodynamic assessments should be performed on the actual administration day of daratumumab, not on the original scheduled administration day.

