9.2. Discontinuation of Study Treatment/Withdrawal From the Study

Discontinuation of Study Treatment

If a subject's study treatment must be discontinued, it will not result in automatic withdrawal of the subject from the study. The EoT Visits and Follow-up visit assessments should continue as specified in the [T&E Schedule](#).

A subject's study treatment (daratumumab) should be discontinued if:

- The investigator believes that for safety reasons or tolerability reasons (eg, AE) it is in the best interest of the subject to discontinue study treatment
- The subject becomes pregnant
- The subject withdraws consent for administration of study drug
- The subject initiates treatment with a prohibited medication
- The subject received concurrent (non-protocol) treatment for NKTCL
- The subject experiences unacceptable toxicity, including IRRs described in [Section 5.3](#)

- The subject's dose of daratumumab is held for more than 4 weeks in Cycles 1-6 or for more than 6 weeks in Cycle 7 and beyond (unless sponsor approves continuation)
- The subject experiences PD (see below and [Attachment 6](#)). Relapse from CR is not considered as disease progression.
- Daratumumab becomes commercially available (or when daratumumab can be accessed from another source) for this disease. At this time, the subject will be transitioned from study drug to commercial product and will be withdrawn from the study. In these circumstances, the sponsor and investigator will support transition of the subject to ensure that treatment continues and remains uninterrupted.
- A subject who experiences a second primary malignancy that cannot be treated by surgery or radiotherapy alone must be withdrawn from the study. However, a subject who develops a malignancy that can be cured surgically or with definitive radiotherapy may continue to receive the assigned study treatment and should continue to be followed for subsequent progression of NKTCL.

Subjects should be discontinued from study treatment if they have objective radiological PD based on real time BICR according to LUGANO Classification. Following centrally confirmed radiological PD subjects will be discontinued from study treatment and enter the Follow-up phase.

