10.8. Safety Analyses

Adverse Events

The verbatim terms used in the eCRF by investigators to identify AEs will be coded using the Medical Dictionary for Regulatory Activities (MedDRA). All reported AEs with onset during the Treatment Phase (ie, treatment-emergent AEs, and AEs that have worsened since baseline) will be included in the analysis. For each AE, the percentage of subjects who experience at least 1 occurrence of the given event will be summarized by treatment group.

Summaries, listings, datasets, or subject narratives may be provided, as appropriate, for those subjects who die, who discontinue treatment due to an AE, or who experience a severe or an SAE.

Clinical Laboratory Tests

Laboratory data will be summarized by type of laboratory test. Reference ranges and markedly abnormal results (specified in the Statistical Analysis Plan) will be used in the summary of laboratory data. Descriptive statistics will be calculated for each laboratory analyte at baseline and for observed values and changes from baseline at each scheduled time point. Changes from baseline results will be presented in pre- versus posttreatment cross-tabulations (with classes for below, within, and above normal ranges). Frequency tabulations of the abnormalities will be made. A listing of subjects with any laboratory results outside the reference ranges will be provided. A listing of subjects with any markedly abnormal laboratory results will also be provided.

Parameters with predefined NCI-CTCAE version 4.03 toxicity grades will be summarized. Change from baseline to the worst toxicity grade experienced by the subject during the study will be provided as shift tables. Worst toxicity grade during treatment will be presented, according to NCI-CTCAE (version 4.03). Clinical relevant changes (ie, causing a treatment intervention or need for concomitant therapy) will be also recorded on the AE eCRF. All other lab abnormalities need not be recorded as AEs.

Electrocardiogram (ECG)

Electrocardiogram data will be summarized by ECG parameter. Descriptive statistics will be calculated at baseline and for observed values and changes from baseline at each scheduled time point. Frequency tabulations of the abnormalities will be made.

Vital Signs

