11.3. Procedures

11.3.1. All Adverse Events

All AEs and special reporting situations, whether serious or non-serious, will be reported from the time a signed and dated ICF is obtained until 30 days after the last dose of study drug, unless the subject withdraws consent for study participation, or starts subsequent anticancer therapy. For subjects who have received additional treatment with therapeutic intent for NKTCL during the AE reporting period, only AEs that are considered to be possibly, probably, or definitely related to study drug must be reported (unless the subject has been withdrawn from the study). Serious adverse events (SAEs), including those spontaneously reported to the investigator within 30 days after the last dose of study drug, must be reported using the SAE Form. The sponsor will evaluate any safety information that is spontaneously reported by an investigator beyond the time frame specified in the protocol.

All AEs, regardless of seriousness, severity, or presumed relationship to study drug, must be recorded using medical terminology in the source document and the eCRF. Whenever possible, diagnoses should be given when signs and symptoms are due to a common etiology (eg, cough, runny nose, sneezing, sore throat, and head congestion should be reported as "upper respiratory infection"). Investigators must record in the eCRF their opinion concerning the relationship of the AE to study therapy. All measures required for AE management must be recorded in the source document and reported according to sponsor instructions.

The sponsor assumes responsibility for appropriate reporting of AEs to the regulatory authorities. The sponsor will also report to the investigator (and the head of the investigational institute where required) all suspected unexpected serious adverse reactions (SUSARs).

For all studies with an outpatient phase, including open-label studies, the subject must be provided with a "wallet (study) card" and instructed to carry this card with them for the duration of the study indicating the following:

- Study number
- Statement, in the local language(s), that the subject is participating in a clinical study
- Investigator's name and 24-hour contact telephone number
- Local sponsor's name and 24-hour contact telephone number (for medical staff only)
- Site number
- Subject number
- Any other information that is required to do an emergency breaking of the blind.

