6. SAFETY

Unless specifically stated, the observations that occurred during treatment period (i.e., within 30 days from the last study drug dosing) will be used for safety analyses. All observations will be presented in listings.

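### A subject stopped only by the hold limit can pass the day-37 EoT deadline and the day-30 AE cut-off while still in the Treatment Phase, so new AEs from day 31 are tabulated only if dosing restarts

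*Protocol*

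**What the plan says.** Three clocks run from the last dose.

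- EoT visit (Protocol 3.1, repeated in 8.1.3 and the Time and Events Schedule): "End-of-Treatment (EoT) Visit is to occur within 30 days (+7-day window) after the last dose of all study treatments".
- AE reporting (Protocol 11.3.1): "until 30 days after the last dose of study drug, unless the subject withdraws consent for study participation", or until subsequent anticancer therapy starts.
- Safety analysis (SAP 6): "the observations that occurred during treatment period (i.e., within 30 days from the last study drug dosing) will be used for safety analyses". SAP 6.1 repeats the 30-day limit for AEs, and SAP 2.4 defines the last treatment date as the latest non-zero dose.

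Two other rules run to discontinuation of treatment. Protocol 3.1 says: "The Treatment Phase will extend from Cycle 1, Day 1 until study drug discontinuation". Protocol 10.8 analyses "All reported AEs with onset during the Treatment Phase". Protocol 3.1 also says that safety is monitored during the Treatment Phase and up to 30 days after the last dose.

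The hold rule decides when discontinuation happens. Protocol 9.2 stops treatment if the dose is "held for more than 4 weeks in Cycles 1-6 or for more than 6 weeks in Cycle 7 and beyond (unless sponsor approves continuation"). For a drug-related AE, Protocol 6.1.1 says that a hold of more than 4 weeks (Cycles 1-6) or "more than 6 weeks (Cycle 7 and beyond) will result in permanent discontinuation of daratumumab". Protocol 6.1.2 has a matching rule for holds for other reasons. No section says how the EoT visit or the AE cut-off applies when the hold limit is reached after day 30 or day 37.

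**The concern.** A held subject is still on study treatment by the protocol's own definition, but clocks tied to the last dose keep running. If the hold ends in discontinuation, the last dose turns out to be the one before the hold, and part of the Treatment Phase falls outside both the AE reporting period and the SAP safety window. If dosing resumes, the last dose moves later and the same days fall inside.

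Whether a new event is tabulated then depends on something that happens after it, namely re-dosing, which is itself related to recovery from toxicity. AE collection is also unclear at site level. From day 31 of a hold, the site cannot know whether an event is reportable, because it does not yet know whether the last dose has been given. The EoT visit has a parallel problem: its deadline can pass before there is any decision to end treatment.

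**Working it through.** **Inputs.** Dosing is "weekly for 8 weeks, then every 2 weeks for 16 weeks, then every 4 weeks thereafter" (Protocol 3.2), so the intervals are 7, 14 and 28 days. Hold limits are 4 weeks = 28 days and 6 weeks = 42 days (Protocol 6.1.1, 6.1.2, 9.2). The EoT limit is 30 + 7 = day 37. The AE cut-off is day 30. Days are counted from the last dose on the nominal schedule.

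**Where the hold is counted from.** Protocol 6.1.2 counts the Table 3 limits from the planned administration date. The starting date is not restated for the 4- and 6-week limits, so I took both readings. The rule is *more than* 4 or 6 weeks, so the first day on which it applies is one day past the limit.

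**Reading A, from the planned date.** First trigger day = interval + limit + 1.

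| First held dose | First trigger day | Against day 37 | Days past day 30 | Hold days inside the 30-day window |
|---|---|---|---|---|
| C1D8 to C3D1 | 7 + 28 + 1 = 36 | 1 day before | 6 | days 7-30: 24 of 30 |
| C3D15 to C6D15 | 14 + 28 + 1 = 43 | 6 days late | 13 | days 14-30: 17 of 30 |
| C7D1 | 14 + 42 + 1 = 57 | 20 days late | 27 | days 14-30: 17 of 44 |
| C8D1 onward | 28 + 42 + 1 = 71 | 34 days late | 41 | days 28-30: 3 of 44 |

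The last column counts from the planned date of the held dose to the trigger day, both included.

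**Reading B, from the last dose.** First trigger day = limit + 1.

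- Cycles 1-6: 28 + 1 = day 29, inside both limits.
- Cycle 7 and beyond: 42 + 1 = day 43, which is 6 days past the EoT limit and 13 days past the AE cut-off.

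Cycle 7 and beyond is late on both readings. The 14-day interval is late only on Reading A. The 7-day interval is not late for the EoT visit on either reading.

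The missed-dose and Day 1 rules in Protocol 6.1.1 add a further ambiguity. If within-cycle doses are missed and only the delay of the next Day 1 dose counts towards the limit, the gap in Cycles 1-6 could reach 28 + 28 + 1 = day 57.

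**Illustration of the AE window.** Take 4-weekly dosing and a new AE with onset on day 35 after the last dose. If dosing resumes on day 40 (40 - 28 = 12 days after the planned date, within the Table 3 window and under the 6-week limit on either reading), the last dose is now day 40 or later and the AE is tabulated. If dosing never resumes, the AE is 35 - 30 = 5 days past the cut-off and is left out. Under Protocol 10.8 it would be included in both cases if treatment had not yet been discontinued on day 35.

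**The case against.** The best case against acting has several parts.

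- **The event that causes the hold is normally counted.** AEs are counted by onset. A toxicity that causes a dose to be held exists by the planned dose date, nominally day 28 at the latest, so it normally starts inside the window. It is tabulated, including among AEs leading to discontinuation. This stands. A reader might infer that toxicities which do not recover are removed from the tables, or that hold-period AEs count only in subjects who restart. The documents do not support either: onsets up to day 30 count in everyone, and only new onsets from day 31 differ.
- **A late EoT visit is not inevitable.** Day 36 on the 7-day interval is inside day 37, Reading B puts all of Cycles 1-6 on time, and under Protocol 9.2 the investigator may stop treatment earlier for safety. This stands too. The tempting statement that the visit cannot be on time whenever a hold ends treatment is too strong.
- **Other outputs are less exposed.** Laboratory shift tables run to the EoT visit if that is later (SAP 6.3), all observations are listed (SAP 6), all deaths are summarised (SAP 6.2.1), and Protocol 11.3.2 requires reporting of all SAEs that occur during the study. PK and antibody samples are also due at follow-up week 8, days 42 to 70, which covers trigger days 43 and 57 but just misses 71. A general claim of lost laboratory or antibody data therefore fails. Listings, however, show only what was collected, and Protocol 11.3.1 ends routine AE reporting at day 30. The telephone fallback in 8.1.3 has the same limit.
- **A 30-day window after the last dose is a defensible exposure-based choice, and a discontinuation date is administrative.** That is fair as a matter of design. But Protocol 10.8 and 3.1 already use the Treatment Phase, and the present SAP rule still makes counting of the same off-drug days depend on later re-dosing.

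**Conclusion.** The point holds in a limited form. In Cycle 7 and beyond, a subject stopped solely by the hold limit passes the EoT deadline before the rule takes effect, by 6 days if the hold is counted from the last dose and by 20 or 34 days if it is counted from the planned date. On the 14-day interval the overrun is 6 days, on the planned-date reading only. These figures assume nominal dosing days and no earlier stop by the investigator.

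For AEs, SAP 6 and 6.1 are narrower than Protocol 10.8 and 3.1. New onsets from day 31 of the gap are treated differently according to whether the subject restarts. The gap is widest on 4-weekly dosing, where 3 of 44 hold days count in a subject who stops on Reading A.

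The documents give no frequency for holds this long, so no bias in an AE rate can be calculated. It is probably small: it needs a hold that ends in discontinuation and a new event starting after day 30. For scale, one subject is 1/32 = 3.1% of the two-stage sample. The change is worth making because the documents disagree and the remedy is cheap, not because a large distortion has been shown.

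**What to change.** 1. In SAP 6 and 6.1, and in Protocol 11.3.1 for collection, end the window at the later of last dose + 30 days and the date study treatment is discontinued. This agrees with Protocol 10.8 and 3.1, and hold time then counts the same whether or not the subject restarts. Say which recorded date is the discontinuation date for a stop under the hold rule, because the definition in Protocol 8.1.4 refers to the PD form.
2. Reconcile the EoT timing in Protocol 3.1, 8.1.3 and the Time and Events Schedule with the hold limits in 6.1.1, 6.1.2 and 9.2. State the date from which the 4- and 6-week holds are counted.

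No hold limit or other clinical rule needs to change. The cost is SAP wording and a short protocol clarification. A few off-drug AEs may be added to the tables, so safety rates may look slightly less favourable.

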3.2. Study Design Rationale

Daratumumab Dose Rationale

An established dose regimen of 16 mg/kg (weekly for 8 weeks, then every 2 weeks for 16 weeks, then every 4 weeks thereafter), administered via IV until PD or unacceptable toxicity, was selected based on an acceptable safety profile, clinical activity, and pharmacokinetics consistent with saturation of the target (CD38).

Rationale for Pharmacokinetics and Immunogenicity

Data obtained from the current study will provide information about the pharmacokinetic profile of daratumumab in subjects with NKTCL.

Immunogenicity to daratumumab is possible. Therefore, samples to determine the presence of antibodies to daratumumab (immunogenicity) will be collected from all subjects. The pharmacokinetic assessments collected at all immunogenicity time points will be used to interpret the immunogenicity data. The information from these samples and data from other studies will be used to determine the immunogenicity of daratumumab.

Biomarker Collection

Biomarkers collected in this study will evaluate tumor CD38 levels as a predictive marker of response. Exploratory analysis of Complement Inhibitory Proteins (CIPs, such as CD59, CD55 and CD46) expression from previous studies has indicated that high expression of CIPs might be predictive of lower or lack of response to daratumumab. Therefore, samples collected in this study might evaluate both CD38 and CIPs expression levels by immunohistochemistry (IHC) or immunofluorescent staining. CD38 IHC is a mandatory test, and CIPs staining will be performed whenever samples are available. Specific immune cell subtypes (NK cells, T cells, and B cells) and their subtypes will be analyzed to evaluate the effects of daratumumab on immune cells. This will provide information on potential prognostic markers in NKTCL to better understand this disease, as well as potential markers that predict response to daratumumab.

